We will not use a placebo group. The control condition will consist of visits and phones by study staff to provide social interaction.

- f. Definition of treatment failure or participant removal criteria.

If any participant experiences worsening of depression symptoms (eg. expression of suicidal ideation, worsening PHQ-9 scores that indicate severe depression) then the participant will be referred to professional mental health treatment. Typically, appointments with mental health providers are difficult to obtain immediately. If there is no objection from the participant, the peer will continue the weekly meetings with the participants while he/she waits for the appointment until they complete the 8 meetings.

- g. Description of what happens to participants receiving therapy when study ends or if a participant's participation in the study ends prematurely.

The peer mentor will be guided to anticipate the needs of the participant when the study ends. The peer and the participant will discuss community-based resources and study staff will also assist in linking the participant to both professional depression treatment/services. The same will occur if the participants ends the study prematurely.

5. Drugs/ Substances/ Devices - NA

- a. The rationale for choosing the drug and dose or for choosing the device to be used.
- b. Justification and safety information if FDA approved drugs will be administered for non-FDA approved indications or if doses or routes of administration or participant populations are changed.
- c. Justification and safety information if non-FDA approved drugs without an IND will be administered.

Date: May 20, 2020
Principal Investigator: [name]

6. Study Statistics

a. Primary outcome variables

Primary outcome: The primary outcome will be depression, measured by the Patient Health Questionnaire (PHQ-9). A change of 5 points on the 0 to 27 point PHQ-9 scale corresponds to the minimal clinically important change for an individual.(34) Therefore, an improvement of 5 or more points on the PHQ-9 will be defined as response to the Peer Program. Studies with repeated PHQ-9 measures have shown that practice effects did not result in inability to detect changes in depressive symptoms even when depression was measured on a daily basis. (43, 44)

b. Secondary outcome variables.

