Primary analyses will be intention-to-treat. Descriptive statistics (e.g. frequencies, means, standard deviations, medians, interquartile ranges) and graphic displays will be generated for all study variables to ensure that distributional and other assumptions of the planned analyses are met. We will minimize missing data using our team's documented retention strategies that have resulted in only 14% attrition.³⁷ All primary analyses will be adjusted for sex, demographic factors, life events, medical comorbidity, and use of mental health services. Hypothesis tests will be two-sided with $\alpha=0.05$.

c. Statistical plan including sample size justification and interim data analysis.

Table 3. Assessment schedule														
Variable	Measure	Timing of assessments												
		0 wk	1 wk	2 wk	3 wk	4 wk	5 wk	6 wk	7 wk	8 wk	3 mth	6 mth	9 mth	12 mth
Sociodemographic factors	Self-report	x												
Depression (self-report)	PHQ-9	x	x	x	x	x	x	x	x	x	x	x	x	x
Depression (assessed by clinician)	Mini-International Neuropsychiatric Interview (MINI)	x								x	x	x	x	x
Client engagement	At least 80% attendance of meetings, peer logs of meetings	x	x	x	x	x	x	x	x	x				
Client engagement	Working Alliance Inventory-SR	x	x	x	x	x	x	x	x	x				
Physical, social and emotional function	Medical Outcomes Study Short Form 36	x								x	x	x	x	x
Self-efficacy	General Self Efficacy Scale	x	x	x	x	x	x	x	x	x		x		x
Loneliness	R-UCLA Loneliness Scale	x	x	x	x	x	x	x	x	x		x		x
Coping skills	Brief Copie	x								x	x	x	x	x
Medical comorbidity	WHO WMH CIDI	x								x	x	x	x	x
Clinical and community health service use	Cornell Service Index	x								x	x	x	x	x
New uptake of counseling and antidepressant	Self-report	x	x	x	x	x	x	x	x	x				
Social determinants of Health	Accountable Health Communities Core Health-Related Social Needs Screening Questions	x								x	x	x	x	x

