Our primary study aim is to test the effects of the Peer Enhanced Depression Care Program for reducing depressive symptoms compared to Enhanced Usual Care. H1: Older adults randomized to the Peer Program (vs. control) will report decreased depression (PHQ-9 score decrease ≥ 5) at 8 weeks, 3, 6, 9 and 12 months. To assess the immediate effects of treatment, we will fit a mixed effects model(59) with nested random effects for counselor and participant such that $E[y_{ij}] = \beta_0 + \beta_1 tx + \beta_2 week + \beta_3 tx * week$, adjusted for sex and other covariates (see 7.a.), where y_{ij} is the PHQ9 score for the i th individual at intervention week j , β_2 is the rate of change in PHQ-9 for individuals randomized to EUC, and β_3 , the coefficient of interest, is the difference in rates of change in PHQ-9 between the Peer Program and Enhanced Usual Care study arms. To assess durability of the intervention effects, we will model PHQ-9 at each post-intervention follow-up (months 3,6,9 and 12) using a time-averaged model, which adjusts for PHQ-9 at week 8 and models PHQ-9 scores at later time points as a function of treatment assignment.

Sample size and power

We calculated power to detect a difference in rate of PHQ-9 decline over the 8-week intervention period via simulation. Assuming 20% attrition, design effect of 1.2 (to account for clustering within peers (62) based on ICCs from pilot data), and regression parameters from our preliminary data (SD of random intercept: 2.83; SD of random errors: 0.11), with N=160, we would have 99% power to detect a difference in slope of 0.625, which corresponds to a between-group difference of 5 points on the PHQ-9 at 8 weeks. Similarly, we calculated power to detect a sustained post-intervention between-group difference. We will have 99% power to detect a sustained 5-point difference in PHQ-9 during that period.

Data and safety monitoring plan

We will have a Data and Safety Monitoring Board (DSMB) to monitor the study with an attendant monitoring plan that will involve interim analysis. We will provide descriptive data for the first 6 months after the first participant has enrolled in the study to review both the non-serious and serious adverse event rates. We will meet every 6 months and also meet on an ad hoc basis if the real time serious adverse events warrant meeting, in their judgment.

d. Early stopping rules.

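### H1 claims a benefit at five time points, but the plan has one slope test and one time-averaged test, unranked and with no success rule, so H1 is only partly tested

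*Combined protocol and SAP*

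**What the plan says.** - **Hypothesis.** Section 2 (Objectives) and section 6.c both state H1: the peer arm, compared with control, "will report decreased depression (PHQ-9 score decrease ≥ 5) at 8 weeks, 3, 6, 9 and 12 months".
- **Primary outcome.** Section 6.a says "The primary outcome will be depression, measured by the Patient Health Questionnaire (PHQ-9" and attaches no time point. It adds that "an improvement of 5 or more points on the PHQ-9 will be defined as response to the Peer Program", but no analysis of that response variable follows.
- **First test.** For immediate effects, section 6.c fits a mixed model to PHQ-9 over the intervention weeks. Its treatment-by-week term, β3, is called "the coefficient of interest, is the difference in rates of change in PHQ-9" between the arms.
- **Second test.** For durability, section 6.c says "we will model PHQ-9 at each post-intervention follow-up (months 3,6,9 and 12) using a time-averaged model", with adjustment for PHQ-9 at week 8.
- **Error level.** The analysis paragraph just before section 6.c says "Hypothesis tests will be two-sided with" an alpha of 0.05. This is the only rule on error rates in the document.
- **Power.** Under Sample size and power, each of the two comparisons is given 99% power with 160 participants.

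The document does not name a primary time point. It does not say which model decides the trial, in what order the tests are taken or how alpha is shared. Nor does it say whether one part of H1 or all of it must succeed.

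**The concern.** There are two separate gaps.

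The first is between the hypothesis and the tests. A time average over months 3 to 12 gives one number. It can be significant because of a large early difference that has gone by month 9 or 12, so it cannot support a separate statement about each visit. H1 makes exactly those statements.

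The second is the missing decision rule. Two tests serve the same primary aim, each at the full 0.05. Calling β3 the coefficient of interest ranks terms within the first model; it does not rank the first model against the second. If the slope is significant and the average is not, or the reverse, the plan does not say whether the trial is positive. That choice could then be made after the results are seen.

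**Working it through.** **Inputs from the plan.** N = 160, allocated 1:1; attrition 20%; design effect 1.2; random-intercept SD 2.83; residual SD 0.11; slope difference 0.625 points per week; sustained difference 5 points; alpha 0.05 two-sided.

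**1. The plan's own power.** Effective n per arm = 160 × 0.8 / 1.2 / 2 = 53.3.
- Slope: the sum of squared deviations of weeks 0–8 is 60, so the SD of a participant's slope is 0.11/√60 = 0.0142. A difference of 0.625 then has power above 0.999.
- Follow-up mean, not adjusted for week 8: SD = √(2.83² + 0.11²/4) = 2.83. A difference of 5 has power above 0.999.

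The stated 99% is reproduced for both.

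**2. What each test covers.**
- Week 8: randomisation makes the expected week-0 difference zero, so under a linear trend the week-8 difference is 8 × β3. With the planned value this is 8 × 0.625 = 5 points, so this part of H1 is tested if the trend is linear.
- Months 3, 6, 9 and 12: there is one averaged coefficient. As an illustration, differences of 5, 5, 0 and 0 average (5 + 5 + 0 + 0)/4 = 2.5, the same as a constant 2.5 at all four visits. The test cannot tell these apart.

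**3. Error rate under each possible success rule, two tests at 0.05.**
- Either suffices: 1 − 0.95² = 0.0975 if independent; upper bound 0.05 + 0.05 = 0.10.
- Both required: at most 0.05.
- Fixed sequence, durability tested only after a significant slope: 0.05.
- Alpha split equally: 1 − 0.975² = 0.049 if independent.

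The either-suffices case was also simulated: 20,000 null trials, 64 per arm (160 × 0.8 / 2), with a t-test on participant slopes and an analysis of covariance of the follow-up mean on arm and week-8 PHQ-9. Clustering and the other covariates were ignored. The error was 0.093 with the stated SDs. With an assumed residual SD of 3 it was 0.095 without a random slope and 0.099 with a random-slope SD of 0.4.

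**4. What the week-8 adjustment does to the durability test.** Suppose a 5-point difference is present at week 8 and simply persists. With a random intercept only, the week-8-adjusted coefficient is 5 × (1 − ρ), where ρ = 2.83²/(2.83² + residual variance).
- Stated residual SD 0.11: ρ = 8.0089/8.0210 = 0.9985, so the coefficient is about 0.0075. Simulation (4,000 trials, 53 per arm) gave 0.007 in size and about 5% power.
- Assumed residual SD 3: ρ = 8.0089/17.0089 = 0.471, so the coefficient is about 2.6; simulated power 99.5%.
- Assumed residual SD 3 with random-slope SD 0.4: simulated coefficient 1.6, power 74%.

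The written model therefore measures change beyond week 8. The stated 99% for a sustained 5-point difference matches a comparison without the week-8 adjustment.

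**The case against.** The strongest reply is that the plan implies a hierarchy. Immediate effects come first, durability second, and power is worked out first for the slope. H1 also joins its time points with *and*, which can be read as requiring all of them. Under either reading the error is at most 5%. This stands as far as it goes: inflation follows only from a success rule that the plan does not state. But the ordering is a hint and not a rule, and the two readings give different verdicts when the tests disagree.

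A reader might go further and infer that H1 is not tested at all. The documents do not support that. The slope is tied explicitly to a 5-point difference at 8 weeks, and the follow-up model addresses months 3 to 12 jointly. The phrase "model PHQ-9 at each post-intervention follow-up (months 3,6,9 and 12) using a time-averaged model" even leaves open whether visit-specific estimates will be reported.

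A reader might also charge the plan with the error of five visit-wise tests: 1 − 0.95⁵ = 22.6% if independent. The plan contains no such tests, so that figure does not describe it. With correlated visits, simulation gives 5.6% on the stated SDs and 15–19% on the assumed ones.

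Finally, one could argue that the two planned tests are so correlated that the inflation is smaller, for example about 7.9% at an assumed correlation of 0.8. Nothing in the documents supports that correlation, and simulating the two tests gives 9.3–9.9%.

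**Conclusion.** The point holds in a limited form. H1 as worded is only partly tested: week 8 is covered under linearity, months 3 to 12 are covered as an average, and no month is tested separately. The primary test, its time point and the success rule are unstated. If either test may count, the family-wise error is about 9–10%; it would be wrong to say that the trial's error rate is necessarily inflated, because another rule would hold it at 5% or below.

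The absence of a ranking and the mismatch with H1 can be read directly from the text and rest on no assumption. The 9–10% assumes that either test suffices, and the simulated part ignores clustering and other covariates. The effect of the week-8 adjustment depends strongly on the residual SD: on the stated 0.11 it removes nearly all of a sustained difference, and on an assumed 3 it removes about half or more. The stated 0.11 looks very small for a 0–27 scale, so power figures built on it are weak support. At an assumed residual SD of 8, slope power would be 0.88 at alpha 0.05.

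This should be settled before outcome data are analysed.

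**What to change.** 1. Name one primary test. The slope already powered in section 6.c is sufficient if reported as the week-8 between-arm difference, 8 × β3, with its confidence interval. Replacing it with a directly estimated week-8 mean difference is possible but not needed to solve this problem.
2. Test durability second, at two-sided 0.05, only if the first test is significant.
3. Report the between-arm differences at months 3, 6, 9 and 12 with confidence intervals, as estimates and not as further confirmatory tests. PHQ-9 is already scheduled at each of these visits.
4. Adjust the durability model for baseline PHQ-9 in place of week-8 PHQ-9, so that it addresses a sustained difference. Otherwise, reword its claim as change after week 8.
5. Reword H1 to match, and say whether the 5-point threshold refers to a mean difference or to individual response. If it is response, add the analysis.

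The cost is protocol and SAP wording, plus restating follow-up power for whichever durability model is kept. The primary test stays at 0.05, so no extra patients are needed for the ordering. The downside is that durability cannot be claimed if the first test fails.

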Randomization procedures. After a clinical and with informed consent, eligible clients will be randomized in a 1:1 ratio, to receive either: (1) the Peer Enhanced Depression Care Program or (2) Social Interaction Control. We will use MS Excel VBA-based software developed by the study statistician to allocate participants using dynamic urn minimization to balance study arms by sex.⁽³⁵⁾ These procedures will maintain allocation concealment throughout the trial, consistent with the CONSORT recommendations.⁶⁹ At the time of randomization, primary care physicians will be informed of the client's assignment with consent of the participant.

The intervention: PEERS. In our program trained and supervised older peer mentors with experiential knowledge of depression and self-care skills deliver depression care to low-income and minority older adults. The primary role of the peer mentors is to build relationship, provide emotional support, facilitate simple goal setting, share coping skills and depression self-care skills and connect to clinical and community resources for depression upon completion of the program. The program is relationship-based and takes an empowerment strategy to increase self-efficacy in depression self-care.⁽³⁶⁾ We use strategies to enhance cultural appropriateness of our program for minority and low-income older adults such as avoiding stigmatizing clinical language about mental health, respecting non-medical self-

care methods such as religious coping, taking a non-judgmental attitude, accommodating client preferences, being aware of the impact of hierarchy and power relations.(37) The peer mentor will be supervised by a licensed clinical social worker.

Matching and scheduling of visits. Once the randomization has been completed, the older adults will be informed of their assignments. The social worker will call the peer mentors to provide contact information and brief summary of the older adult with whom they are matched. Then the peer mentors will contact the older adult and set a time and place for the meeting. Peer mentors will meet with older adults for 8 meetings weekly for 45 minutes to an hour each. Each meeting will be audio-recorded. Meetings will be by telephone.

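### The primary model leaves the week 0 arm difference free and does not give week 0 PHQ-9 a role, so it may forgo precision; this affects efficiency, not validity

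*Combined protocol and SAP*

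**What the plan says.** Section 6.c gives the mean of PHQ-9 as β0 + β1·tx + β2·week + β3·tx·week. For this, "we will fit a mixed effects model(59) with nested random effects for counselor and participant"; no random slope is mentioned. β1, the arm difference at week 0, is unconstrained. The target is β3, "the coefficient of interest, is the difference in rates of change in PHQ-9 between the Peer Program and Enhanced Usual Care study arms".

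The outcome "is the PHQ9 score for the i th individual at intervention week j". Table 3 collects PHQ-9 at week 0, weekly to week 8, and at months 3, 6, 9 and 12. The plan does not say whether the week 0 score is an outcome row.

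Section 4.a (Clinical assessment) places the baseline assessment before randomization. Allocation is balanced on sex only.

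On covariates, the paragraph just before section 6.c says: "All primary analyses will be adjusted for sex, demographic factors, life events, medical comorbidity, and use of mental health services". The Covariates paragraph in section 6.b adds, among others, past and current depression treatment. Neither names baseline PHQ-9. The model text refers to 7.a for its covariates, but section 7.a covers medical risks.

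The month 3–12 model adjusts for week 8 PHQ-9. No adjustment for baseline PHQ-9 is stated there either.

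**The concern.** The arms cannot differ systematically on a score taken before randomization. Estimating β1 therefore spends information on a quantity known to be zero in expectation. Intercept and slope estimates are correlated, so that uncertainty carries into β3. If week 0 is not an outcome row, the model loses the earliest time point as well, and baseline PHQ-9 is then not used at all.

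At stake is the width of the confidence interval for β3, and power if the true effect is smaller than the planned 0.625 points per week. In the month 3–12 model the target is a difference in level between people, so a baseline score taken before randomization is a natural covariate, and it is missing.

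**Working it through.** **Inputs from section 6.c.** N = 160, 20% attrition, design effect 1.2, random-intercept SD τ = 2.83, residual SD σ = 0.11, slope difference 0.625 per week. Allocation is 1:1 (section 4.a) and α is 0.05 two-sided (section 6). Every residual SD other than 0.11 below is an assumption.

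**The plan's own power.** Effective n per arm = 160 × 0.8 / 1.2 / 2 = 53.3. For weeks 0–8, Σ(week − 4)² = 60. With β1 free:

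- SE(β3) = σ·√(2/(n·60)) = 0.11 × √(2/(53.3 × 60)) = 0.11 × 0.025 = 0.00275
- Power = Φ(0.625/0.00275 − 1.96) ≈ 1.000

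This is consistent with the stated 99% but not a sharp match; exactly 99% would need σ of about 5.8.

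**Effect of a common week 0 mean.** With balanced data and a random intercept, let k = σ²/(σ² + 9τ²), where 9τ² = 9 × 2.83² = 72.08. Then

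- Var(β3), β1 free = 2σ²/(60n)
- Var(β3), β1 = 0: 2σ²/(n(60 + 144k))
- Relative reduction = 144k/(60 + 144k)

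Example at σ = 2: k = 4/76.08 = 0.0526, 144k = 7.57, reduction = 7.57/67.57 = 11.2%.

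| Residual SD | SE, β1 free | SE, β1 = 0 | Variance cut | Cut with uncorrelated random slope SD 0.5 |
|---|---|---|---|---|
| 0.11 (plan) | 0.00275 | 0.00275 | 0.04% | 0% |
| 1 | 0.0250 | 0.0246 | 3% | 0.2% |
| 2 | 0.0500 | 0.0471 | 11% | 2% |
| 3 | 0.0750 | 0.0667 | 21% | 8% |
| 4 | 0.1000 | 0.0835 | 30% | 16% |
| 5.02 | 0.1255 | 0.0986 | 38% | 24% |

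The last row takes the pilot's SD of 7.1 (section 3) to be the SD of PHQ-9 change, so σ = 7.1/√2 = 5.02. If slopes and intercepts are correlated, the gain moves either way: at slope SD 0.5 and σ = 3 it is 37% at correlation −0.5 and 1% at +0.3.

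**Power.** Under the random-intercept model with weeks 0–8 and β1 free, power for 0.625 is at least 99.8% in every row. If week 0 is left out, it is still 98.6% at σ = 5.02. For a smaller effect the gain is visible: at σ = 3, the slope difference for which the free model has 80% power is 0.210 per week (0.210 × 8 = 1.68 points at week 8), and the constraint raises that power to 88%.

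**Weeks 1–8 with baseline as a main-effect covariate.** In balanced data such a covariate changes only between-person variance and leaves SE(β3) as it was. Dropping week 0 as an outcome lowers the sum of squares from 60 to 42. Against the weeks 0–8 model with β1 free, the variance ratio is 60/42 = 1.43: a 43% increase at every σ under a random-intercept model.

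**What the constraint costs.** With linear week, β1 = 0 forces the effect through zero at week 0. For a 5-point effect complete by week 1, the free slope is −20/60 = −0.33 and the constrained slope is −(20 + 160k)/(60 + 144k): −0.42 at σ = 2 and −0.50 at σ = 3. For an effect that starts after week 4 and reaches 5 points at week 8, the free slope is −37.5/60 = −0.625 and the constrained slope is −(37.5 + 50k)/(60 + 144k): −0.59 and −0.57.

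**Month 3–12 model.** Take the mean of the four follow-ups under the random-intercept model. Its residual variance is τ²σ²/(τ² + σ²) + σ²/4 given week 8 alone, and τ²σ²/(2τ² + σ²) + σ²/4 given week 8 and week 0. At σ = 2 this goes from 3.67 to 2.60, a cut of 29%. At σ = 5 it goes from 12.3 to 11.1, a cut of about 10%.

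**The case against.** The strongest reply is that on the plan's own variance figures the gain is 0.04%, and that larger gains need residual SDs the documents do not state. The arithmetic stands. But 0.11 is hard to accept as a residual SD for an integer score from 0 to 27: rounding alone gives 1/√12 = 0.29. It also sits badly with a pilot SD of 7.1, if that is the SD of change. The size of the gain is therefore uncertain, not known to be nil.

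Three further replies hold. First, β3 is a within-person contrast, so stable differences between the arms at baseline are absorbed by β1. A reader might infer that chance baseline imbalance biases the result, or that the trial is underpowered without the change; the documents support neither. Second, a reader might infer that adding baseline PHQ-9 to the covariate list of the weekly model would cure the problem. For β3 it would not, and moving week 0 out of the outcome to do so would lose precision. Third, the constraint is not free, because it changes what a linear slope estimates when the effect is not linear.

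The constraint also cannot be carried over to months 3–12. There the treatment term is the effect of interest and must stay; only a baseline covariate makes sense.

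**Conclusion.** The point holds as a matter of efficiency and pre-specification. The model leaves a difference free that randomization makes zero in expectation, the role of week 0 PHQ-9 is unstated, and the pointer to the covariates leads to the wrong section. The planned estimator is valid and the stated power is not at risk.

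The gain from a common week 0 mean is negligible at the plan's residual SD of 0.11, 3% of variance at SD 1, and 11% to 38% at assumed SDs of 2 to 5 with a random intercept only. It is generally smaller with uncorrelated random slopes. In the month 3–12 model, baseline PHQ-9 cuts the residual variance given week 8 by about 10% to 29% at assumed SDs of 5 to 2. These figures assume balanced data, a linear trend from week 0, an intercept SD of 2.83, and the 1.2 design effect applied to both arms.

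**What to change.** In section 6.c:

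1. State that week 0 PHQ-9 is an outcome row, and fit weeks 0–8 with one week 0 mean common to both arms (no treatment main effect).
2. Report the model with β1 free as a sensitivity analysis, to show whether the slope estimate depends on the effect being linear from zero.
3. Do not replace this with a weeks 1–8 model that has baseline PHQ-9 as a main-effect covariate.
4. Add baseline PHQ-9 as a covariate in the month 3–12 model and keep its treatment term.
5. Correct the 7.a reference so that it leads to the covariate list.

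This takes a few lines of text and one extra model fit, with no new data. The statistical cost is the linearity dependence shown above, which item 2 makes visible. The constraint also relies on the week 0 score being taken before randomization in every case, as section 4.a provides.

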
2. Objectives (include all primary and secondary objectives)

The specific aims of this proposal are as follows:

- (1) To measure the effect of a peer mentoring program on mild to moderate depression compared to social interaction control among minority and low-income adults aged 50+ years recruited from primary care clinics;
H1: Older adults randomized to the Peer Program (vs. control) will report decreased depression (PHQ-9 score decrease ≥ 5) at 8 weeks, 3, 6, 9 and 12 months.

We will conduct a randomized controlled trial by enrolling 160 low-income and minority adults and measure the effect of the Peer Enhanced Depression Care Program on mild to moderate depressive symptoms compared to Social Interaction Control. We will recruit a total of 10 peer mentors. The supervised peer mentors who are based in the community will provide social support by telephone with depressed older adults recruited from primary care and the

community for 8 weeks with initial training and ongoing supervision by a clinical social worker. The core components of the Peer Program are: (1) relationship building, active listening, emotionally responsive and patient-centered communication, (2) sharing of experiential knowledge by peer mentors, sharing of coping skills, modeling and communication of positive health messages regarding self-care (3) linkage to community and clinical mental health resources. In Aim 2, we will conduct a quantitative mediation analysis, specifically measuring increase in self-efficacy as the mediating factor. In Aim 3, we will use post-study key informant interviews from a diverse group of stakeholders representing individuals, the community and the primary care clinic to assess implementation process, and we will use checklists to evaluate the fidelity of the intervention.

3. Background (briefly describe pre-clinical and clinical data, current experience with procedures, drug or device, and any other relevant information to justify the research)

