We conducted a study that showed ethnic disparity in use of psychotherapy offered in primary care for African American older adults with depression. We capitalized on depression screening and clinical diagnostic assessments that occurred in PROSPECT.(25, 26) We focused on the 582 persons with complete data assessed at baseline.(27) Compared to White older adults, persons who self-identified as African-American were less likely to have received Interpersonal Psychotherapy if they had minor depression even after adjusting for potentially influential covariates (AOR)=0.22, 95% confidence interval (CI)=0.06-0.80). African Americans were less likely to receive psychotherapy than Whites among persons who met criteria for major depression as well. While the intervention “raised all boats,” the ethnic disparity persisted even in the intervention practices. Focus on the clinical setting may improve health but not health disparities. A model that is accessible in the community and linked to clinics may be more effective in mitigating health disparities over clinical approaches alone.

We developed a peer intervention and evaluated the feasibility and acceptability of peer mentors for older adults and examined client and peer experiences of the program. We found that engagement was high (90% percent of older adults attended all 8 meetings with the peer). The majority was African American older adults (74%) and 85% had decrease in PHQ-9 scores [Mean 7.1 (SD 7.1) p-value < 0.001].(28) Loneliness decreased (pre-study mean 36.7 ± 5.4 ; post-study mean 31.4 ± 16.7 , p-value 0.03) and coping skills increased (pre-study mean 65.6 ± 13.2 , post-study mean 69.9 ± 10.4 , p-value 0.006). Older adults emphasized the importance of a trusting relationship, credibility of the peer and usefulness of professional supervision in the program. Participants described benefits such as hope, changes in attitude, behavior and insight. The program also successfully connected older adults to community and clinical resources during and after the study.

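### The only month 3–12 PHQ-9 model adjusts for week-8 PHQ-9, a post-randomization outcome, so it does not estimate the sustained arm difference for which 99% power is claimed

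*Combined protocol and SAP*

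**What the plan says.** H1 (section 2, repeated in section 6.c) is that the peer arm, compared with control, "will report decreased depression (PHQ-9 score decrease ≥ 5) at 8 weeks, 3, 6, 9 and 12 months". Four of those five time points fall after the intervention.

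Section 6.c splits the analysis in two. For weeks 0 to 8: "To assess the immediate effects of treatment, we will fit a mixed effects model(59) with nested random effects for counselor and participant", with the arm-by-week slope as the quantity of interest. For months 3, 6, 9 and 12, under the label of durability, it specifies a "time-averaged model, which adjusts for PHQ-9 at week 8 and models PHQ-9 scores at later time points", with treatment assignment as the predictor.

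The sample-size text assumes a slope difference of 0.625 points per week, "which corresponds to a between-group difference of 5 points on the PHQ-9 at 8 weeks". For follow-up it adds: "We will have 99% power to detect a sustained 5-point difference in PHQ-9 during that period". That second calculation is introduced only as similar to the first. It has no model or inputs of its own.

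The document as supplied contains no unadjusted or baseline-adjusted comparison of the arms at months 3 to 12. The general covariate list at the end of section 6.b does not name baseline PHQ-9.

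**The concern.** Week-8 PHQ-9 is a result of the treatment. Holding it fixed removes from the later arm difference whatever part the week-8 difference predicts, and participants matched on week-8 score are no longer a randomized comparison. The plan would then report a fully maintained benefit as smaller than it is, by an amount that depends on a slope stated nowhere. If the benefit fades in part, the model could show no effect, or an effect favouring control, while the peer arm still has lower PHQ-9.

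The 99% power is claimed for a sustained difference between the arms, which this coefficient does not measure. The week 0–8 slope analysis is not affected.

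**Working it through.** **Inputs from the document.** N = 160, attrition 20%, design effect 1.2 and week-8 arm difference 0.625 × 8 = 5 points (section 6.c); two-sided α = 0.05 (section 6.b); 1:1 allocation (section 4.a). Effective n per arm = 160 × 0.8 / 2 / 1.2 = 53.3. The variance inputs are "SD of random intercept: 2.83; SD of random errors: 0.11".

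**The plan's own figure.** For the plain arm difference in the four-visit mean on these inputs, SE = √[(2.83² + 0.11²/4) × 2/53.3] = 0.548. Then 5/0.548 = 9.1, and power is above 99.9%. The claimed 99% is therefore met, but for the difference without conditioning on week 8.

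**What the stated model estimates.** Let D be the true arm difference at months 3–12 and b the within-arm slope of later PHQ-9 on week-8 PHQ-9, so that b = ρ × SD(later)/SD(week 8). With a week-8 difference of 5,

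coefficient = D − 5b.

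If D = 5 this is 5(1 − b), below 5 for any positive b. It is zero at D = 5b and favours control below that.

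**Size, under assumptions.** The document gives no usable correlation between week 8 and follow-up. I assume total SD 5 at every visit and a random-intercept model with intercept variance si², error variance se² and v = si² + se², so b = ρ = si²/v. Then:

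- residual variance of the four-visit mean: R = si² + se²/4 − si⁴/v
- Var(coefficient) = R × [2/n + 25/((2n − 2)v)], with n = 53.3 per arm

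Example, ρ = 0.7: si² = 17.5, se² = 7.5, R = 17.5 + 1.875 − 12.25 = 7.125. The bracket is 0.0375 + 0.00955 = 0.04705, so SE = √0.3353 = 0.579. With D = 5 the coefficient is 1.5, 1.5/0.579 = 2.59, and power is about 74%.

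Positive values favour the peer arm:

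| ρ | SE | D = 5: coefficient | D = 5: power | D = 3: coefficient | D = 3: significant for peer / for control | D at which coefficient is 0 |
|---|---|---|---|---|---|---|
| 0.3 | 0.673 | 3.5 | 99.9% | 1.5 | 61% / 0% | 1.5 |
| 0.5 | 0.664 | 2.5 | 96% | 0.5 | 11% / 0.3% | 2.5 |
| 0.7 | 0.579 | 1.5 | 74% | −0.5 | 0.2% / 14% | 3.5 |
| 0.9 | 0.368 | 0.5 | 27% | −1.5 | 0% / 98% | 4.5 |

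Simulation (4000 trials per setting, 53 per arm) agrees. For D = 5 it gives mean coefficients of 3.49, 2.50, 1.50 and 0.50 with power 99.9%, 96.2%, 71.3% and 26.5%. For D = 3 it gives 1.51, 0.51, −0.51 and −1.50.

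**Unequal variances.** With ρ = 0.7, week-8 SD 5, later SD 4 / 5 / 6 and D = 5, b = 0.56 / 0.70 / 0.84. The coefficient is 2.2 / 1.5 / 0.8, with simulated power 99.7% / 73% / 21%.

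**Baseline adjustment instead.** In the same simulated trials the mean coefficient is 4.99 to 5.01 when D = 5 (power 100%) and 2.99 to 3.02 when D = 3 (power 99.8% to 100%).

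**The plan's SDs taken literally.** ρ = 2.83²/(2.83² + 0.11²) = 0.9985, so for D = 5 the coefficient is 0.0075, SE 0.032, power about 6%. I do not offer this as a forecast, because the 0.11 is doubtful. It implies an SD of change of √2 × 0.11 = 0.16, while section 3 reports that "85% had decrease in PHQ-9 scores [Mean 7.1 (SD 7.1) p-value < 0.001", which, if the bracket describes the decrease, is an SD of 7.1.

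**The case against.** Conditioning on week 8 is a declared choice. The model is labelled as a durability analysis and kept apart from the immediate-effects model. It answers a real, narrower question: given where treatment left people, do the arms differ later? If a benefit falls from 5 to 3 points, a null or negative coefficient is partly a signal of that loss. This stands as a reason to keep the model as an additional analysis. It does not make the model a test of H1 at months 3–12, because a null result is also compatible with a benefit that has largely or fully lasted.

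No power failure is shown. At correlations of 0.3 to 0.5 a fully sustained effect still gives 96% to 99.9%. That is correct; the case rests on the wrong contrast, not on the power columns.

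The illustrations can be disputed. With equal visit SDs of 5, a change SD of 7.1 would imply ρ = 1 − 7.1²/(2 × 25), about 0. The higher correlations would need visit SDs of about 9.2 (ρ = 0.7) or 15.9 (ρ = 0.9). Correlation may also fall over the year, which would lower the average b. Both points caution against reading the high-ρ rows as predictions. However, the pilot change runs from before to after treatment, not from week 8 to follow-up, and neither point alters D − 5b.

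Finally, the follow-up power simulation is not described, so it may have targeted a 5-point coefficient conditional on week 8; the 99% alone cannot rule that out. Such a coefficient requires D = 5 + 5b, more than 5 for any positive b and about 10 on the plan's own SDs. That is not a 5-point difference being sustained.

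**Conclusion.** The concern holds. With H1 read as a comparison of means, four of its five time points have no analysis of the randomized arm difference, and the 99% follow-up power refers to a contrast that the planned model does not estimate. (If H1 is read as response, a drop of 5 or more, this model does not estimate that either; that is a separate point.)

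The direction follows from algebra: given the plan's 5-point difference at week 8 and any positive b, the coefficient understates the follow-up difference by 5b. The amount is not known from the document. Over assumed correlations of 0.3 to 0.9 with SD 5, a maintained 5 points is reported as 3.5 down to 0.5. A remaining 3 points is reported as anything from 1.5 in favour of the peer arm to 1.5 in favour of control. A loss of power is possible but not established. This should be corrected before analysis, because it can attenuate or reverse the long-term conclusion on the primary outcome.

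**What to change.** - In the month 3–12 model, replace week-8 PHQ-9 with baseline (week-0) PHQ-9. Report the time-averaged arm difference, with the differences at months 3, 6, 9 and 12 as supportive.
- State the participant and counselor random effects for this model. Section 6.c gives them only for the immediate-effects model.
- If a week-8-adjusted model is kept, label it exploratory and describe its coefficient as the arm difference conditional on week-8 PHQ-9.
- Recompute the follow-up power for the revised model with its own stated inputs, after rechecking the error SD of 0.11.

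The cost is SAP wording and one rerun of the power calculation. No new data are needed, since Table 3 already schedules the PHQ-9 at week 0.
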